7.0 Demographics, Baseline Characteristics, Medical History, and Other Medications

The ITT population will be used to summarize demographics and baseline characteristics, medical history and previous, concomitant, and post-treatment medications; data will be summarized across all subjects and by assigned treatment arm. Demographics and baseline characteristics will also be summarized by GT.

7.1 Demographic and Baseline Characteristics

Categorical demographic and baseline characteristic variables will be summarized with the number and percentage of subjects in each category. Continuous variables will be summarized with descriptive statistics (number of non-missing observations, mean, standard deviation, median, maximum and minimum). For categorical variables, the number of missing observations will be displayed, if applicable, on the summary tables. Percentages will be calculated based on the number of non-missing observations.

Continuous demographic variables include age, weight, height, waist circumference, and body mass index (BMI). Categorical demographic variables include sex, race, Asian race (Asian or non-Asian), types of Asian race (as captured in the eCRF form 'Demographics': Japanese, Chinese, Korean, Taiwanese, and Other, which can include Vietnamese, Burmese, Cambodian, etc.), ethnicity, age category (< 65 or ≥ 65 years; < 75 or ≥ 75 years), BMI category (< 30 or ≥ 30 kg/m²), country, and geographic region (North America, Europe, Asia, or rest of world [ROW]).

When defining geographic region, sites in the United States and Canada will be grouped under North America; sites in Belgium and France will be grouped under Europe; sites in

Singapore and Vietnam will be grouped under Asia; sites in Australia, New Zealand and South Africa will be grouped as ROW.

Continuous baseline characteristics include baseline \log_{10} HCV RNA level, homeostasis model of assessment – insulin resistance (HOMA-IR), creatinine clearance (Cockcroft-Gault calculation), eGFR (using the modification of diet in renal disease [MDRD] formula), platelet count, albumin, GGT, LDL, HDL, APRI, FIB-4, AST, ALT, total, direct, and indirect bilirubin.

Categorical baseline characteristics include:

- HCV GT (5, or 6) and available subtype (as determined by the central laboratory);
- Cirrhosis status (cirrhotic or non-cirrhotic);
- Prior HCV treatment history (naïve or experienced);
- For treatment-experienced subjects, type of previous regimen (IFN- or SOF-based);
- For treatment-experienced subjects, type of non-response to previous treatment (on-treatment non-responder, breakthrough, post-treatment relapse, or unknown/other);
- IL28B genotype (CC, CT, or TT; CC or non-CC);
- Baseline HCV RNA level ($< 1,000,000$ or $\geq 1,000,000$ IU/mL, $< 2,000,000$ or $\geq 2,000,000$ IU/mL);
- Baseline fibrosis stage (equivalent to Metavir F0 - F1, F2, F3, or F4);
- Baseline platelet count (< 90 or $\geq 90 \times 10^9/L$);
- Baseline albumin (< 35 or ≥ 35 g/L);
- Baseline creatinine clearance (< 60 , ≥ 60 to < 90 , ≥ 90 mL/min);
- Baseline eGFR (< 90 , ≥ 90 mL/min/1.73 m²);
- History of diabetes (yes/no);
- History of bleeding disorders (yes/no);
- History of depression or bipolar disorder (yes/no);

- History of cardiovascular disease (yes/no);
- Baseline metabolic syndrome (yes/no);
- Injection drug use (yes, within last 12 months; yes, more than 12 months ago; or no);
- Use of stable opiate substitution (yes/no);
- Concomitant use of Proton Pump Inhibitors (PPIs) (yes/no);
- Tobacco use (current, former, never, or unknown);
- Alcohol use (current, former, never, or unknown).

In addition, for cirrhotic subjects, the following will be summarized:

- Baseline Child-Pugh score (5, 6, or > 6).

Summaries of baseline resistance are described in Section 10.8.

For treatment-experienced subjects, any regimen that contains SOF with or without IFN or RBV is SOF-based. Otherwise, any regimen that contains IFN with or without RBV is IFN-based.

Any concomitant medication coded to the WHO Drug Dictionary ATC code of A02BC will be counted as a PPI.

If the IL28B genotype result is not available from a sample collected during the Screening period, then a result available from a sample collected at any time during the study will be used to summarize IL28B genotype. IL28B rs12979860 will be resulted as C/C, C/T, or T/T by the central laboratory.

HOMA-IR is defined as $\text{fasting glucose (mmol/L)} \times \text{fasting insulin } (\mu\text{IU/mL}) \div 22.5$. Subjects who do not have concurrent fasting glucose and fasting insulin values at baseline will be excluded from the summary of baseline HOMA-IR.

Baseline fibrosis stage is defined for subjects with non-missing liver biopsy scores, FibroScan scores, or FibroTest scores. Only one score will be used to categorize each

subject even if a subject has more than one score recorded. If a biopsy score is present, then it will be used to categorize the subject, regardless of the FibroScan/FibroTest score. Similarly, if a FibroScan score is present along with a FibroTest score, then the FibroScan score will be used to categorize the subject. If biopsy and FibroScan scores are not present and more than one FibroTest result is available, then the baseline FibroTest result (i.e., last non-missing FibroTest result on or before Day 1) will be used to categorize the subject. Subjects will be categorized as F0-F1, F2, F3, or F4 according to [Table 4](#).

Presence or absence of cirrhosis will be determined as collected in EDC ("What is the subject's cirrhosis status?" – "cirrhotic" or "non-cirrhotic").

Baseline Child-Pugh score is determined by the Day 1 assessment of ascites and hepatic encephalopathy along with the baseline values of total bilirubin, serum albumin, and international normalized ratio (INR). The Child-Pugh score is the sum of the points assigned for each of the five observed findings as defined in [Table 5](#).

Baseline APRI and FIB-4 are defined as the equations below. Subjects who do not have concurrent AST and platelet values at baseline will be excluded from the summary of baseline APRI. Age is defined in years at baseline. Subjects who do not have concurrent values of AST, ALT, and platelet count at baseline, or subjects who are missing age will be excluded from the summary of FIB-4.

$$\text{APRI} = \frac{\text{AST Level (U/L)}}{\text{AST (Upper Limit of Normal) (U/L)}} \times \frac{100}{\text{Platelet Count (10}^9\text{/L)}}$$

$$\text{FIB-4} = \frac{\text{Age (years)} \times \text{AST Level (U/L)}}{(\text{Platelet Count (10}^9\text{/L)} \times \sqrt{\text{ALT (U/L)}})}$$

Table 4. Baseline Fibrosis Stage

Baseline Fibrosis Stage, Metavir Equivalents	Liver Biopsy Metavir, Batts Ludwig, Knodell, IASL, Scheuer, or Laennec Score	Liver Biopsy Ishak Score	FibroScan (kPa)	FibroTest*
F0 – F1	0 or 1	0, 1, or 2	< 8.8	≤ 0.48
F2	2	3	≥ 8.8 to < 9.6	0.49 to 0.58
F3	3	4	≥ 9.6 to < 12.5	0.59 to 0.74
F4	4	≥ 5	≥ 12.5	≥ 0.75

* APRI will not be used to derive Baseline Fibrosis Stage. However, per inclusion/exclusion criteria, subjects need to have concordant FibroTest and APRI scores in order to determine eligibility.

Table 5. Child-Pugh Classification of Severity of Cirrhosis

Parameter	Points Assigned for Observed Findings		
	1	2	3
Total bilirubin, µmol/L (mg/dL)	< 34.2 (< 2)	34.2 – 51.3 (2 – 3)	> 51.3 (> 3)
Serum albumin, g/L (g/dL)	> 35 (> 3.5)	28 – 35 (2.8 – 3.5)	< 28 (< 2.8)
INR	< 1.7	1.7 – 2.3	> 2.3
Ascites*	None	Slight	Moderate to severe
Hepatic encephalopathy**	None	Grade 1 or 2 (or suppressed with medication)	Grade 3 or 4 (or refractory to medication)

* None.

Slight ascites = Ascites detectable only by ultrasound examination.

Moderate ascites = Ascites manifested by moderate symmetrical distension of the abdomen.

Severe ascites = Large or gross ascites with marked abdominal distension.

** None: normal consciousness, personality, neurological examination, electroencephalogram.

Grade 1: restless, sleep disturbed, irritable/agitated, tremor, impaired handwriting, 5 cps waves.

Grade 2: lethargic, time-disoriented, inappropriate behavior, asterixis, ataxia, slow triphasic waves.

Grade 3: somnolent, stuporous, place-disoriented, hyperactive reflexes, rigidity, slower waves.

Grade 4: unarousable coma, no personality/behavior, decerebrate, slow 2 to 3 cps delta activity.

The central laboratory calculates the estimated creatinine clearance (CrCl) based on the following Cockcroft-Gault formula:

$$\text{CrCl (mL/min)} = [(140 - \text{age}) \times (\text{weight in kg}) \times (0.85 \text{ if female})] / [\text{serum creatinine (mg/dL)} \times 72].$$

The central laboratory calculates the eGFR by MDRD based on the following formula:

$$\text{eGFR (mL/min/1.73 m}^2\text{)} = 175 \times (\text{Serum Creatinine})^{-1.154} \times (\text{Age})^{-0.203} \times (0.742 \text{ if female}) \times (1.212 \text{ if Black or African American}).$$

Subjects will be classified as having metabolic syndrome if at least 3 of the 5 characteristics in [Table 6](#) are present.

Table 6. Clinical Identification of Metabolic Syndrome

Risk Factor	Defining Level in Conventional Units	Defining Level in SI Units
Abdominal obesity, given as waist circumference		
Men	> 40 in	> 102 cm
Women	> 35 in	> 88 cm
Triglycerides	≥ 150 mg/dL	≥ 1.695 mmol/L
HDL cholesterol		
Men	< 40 mg/dL	< 1.03452 mmol/L
Women	< 50 mg/dL	< 1.29315 mmol/L
Blood pressure (BP)	Systolic BP ≥ 130 or Diastolic BP ≥ 85 mmHg	Systolic BP ≥ 130 or Diastolic BP ≥ 85 mmHg
Fasting glucose	≥ 100 mg/dL	≥ 5.5507 mmol/L

Reference: Grundy 2004.²

Histories of diabetes, bleeding disorders, depression or bipolar disorder, and cardiovascular disease will be based on the Medical History (MH) eCRF, as defined in [Table 7](#).

Table 7. Medical History eCRF

Subgroup	Medical History eCRF	
	Body System	Condition/Diagnosis
Diabetes	Metabolic	Diabetes mellitus
Bleeding disorders	Blood	Clotting/bleeding problems Factor deficiency Hemophilia Von Willebrand disease
Depression or bipolar disorder	Neurologic and Psychiatric System	Bipolar disorder Depression
Cardiovascular disease	Cardiovascular	Angina Cardiac arrhythmia Cardiovascular disease Congenital heart disease Congestive heart failure Coronary artery disease Hypertension Myocardial infarction Myocarditis Peripheral vascular disease-arterial Peripheral vascular disease-venous Valvular heart disease Vasculitis

7.2 Medical History

Medical history data will be summarized and presented using body systems and conditions/diagnoses as captured on the eCRF. The body systems will be presented in alphabetical order and the conditions/diagnoses will be presented in alphabetical order within each body system. The number and percentage of subjects with a particular condition/diagnosis will be summarized. Subjects reporting more than one condition/diagnosis within a body system will be counted only once for that body system.

7.3 Prior, Concomitant and Post-Treatment Medications

A prior medication is defined as any medication taken prior to the date of the first dose of study drug. A concomitant medication is defined as any medication that started prior to the date of the first dose of study drug and continued to be taken on or after the first dose of study drug or any medication that started on or after the date of the first dose of study drug, but not after the date of the last dose of study drug. A post-treatment medication for the treatment of HCV is defined as any medication taken on or after the last dose of study drug and entered as "Post-treatment HCV medications" on the eCRF.

The number and percentage of subjects taking prior medications, concomitant medications, and post-treatment HCV medications will be summarized by generic drug name based on the WHO Drug Dictionary. The prior HCV medications taken by treatment experienced subjects and collected on the "Last Prior HCV Therapy" and "Second to Last Prior HCV Therapy" eCRFs will be summarized separately from other prior medications, and will not be included in the summaries of all prior and concomitant medications.

8.0 Subject Disposition

The number and percentage of subjects who screen failed for any reason, and for each screen fail reason, will be summarized for all subjects who screen failed.

8.1 Disposition of Safety Population

The number of subjects in each of the following categories will be summarized by investigator for each treatment arm and overall.

- Subjects enrolled in this study;
- Subjects who took at least one dose of study drug;
- Subjects who completed study drug;
- Subjects who prematurely discontinued study drug;
- Subjects who completed the study;

- Subjects who prematurely discontinued from the study;
- Subjects ongoing in the Post-Treatment Period (if applicable at the time of analysis).

The number and percentage of subjects who discontinued study drug will be summarized by reason (all reasons) and by primary reason (per eCRF) for each treatment arm and overall. Similar summaries will be provided for discontinuations from the study.

The number and percentage of subjects with reported study drug interruptions will be summarized by treatment arm and overall. Reasons for study drug interruptions will be presented in the CSR listings.

9.0 Study Drug Exposure and Compliance

Exposure and compliance will be summarized on the ITT population by treatment arm and overall.

9.1 Exposure

Duration of exposure is defined for each subject as the last study drug dose date minus the first study drug dose date plus 1 day.

Descriptive statistics (mean, standard deviation, median, minimum, and maximum) will be presented for duration of exposure during the Treatment Period.

Study drug duration will also be summarized with frequencies and percentages using the following categories:

- 1 to 15 days
- 16 to 30 days
- 31 to 45 days
- 46 to 60 days
- 61 to 75 days
- 76 to 90 days

- > 90 days

In addition, the number and percentage of subjects with study drug duration of ≥ 52 days for Arm A and ≥ 77 days for Arm B will be summarized.

9.2 Compliance

At each visit (starting with the Week 4 visit) during the Treatment Period, the total number of tablets dispensed and returned for each kit is recorded. The compliance for the study drug (GLE/PIB) during the Treatment Period will be calculated as the percentage of tablets taken relative to the total tablets expected to be taken. The total number of tablets expected to be taken will be equal to the total number of tablets that should have been taken per the protocol for the duration that the subject was in the Treatment Period (date of last dose of study drug – date of first dose of study drug + 1). Study drug interruptions recorded on the eCRF will not be subtracted from the duration. If a subject is not able to return any of the dispensed kit, that subject's compliance will be regarded as missing.

A subject is considered to be compliant if the percentage is between 80% and 120%. Compliance will be calculated for each subject and summarized with the mean, median, standard deviation, minimum, and maximum for each treatment arm and overall. A listing of compliance for each subject will be provided. The percentage of compliant subjects will be summarized for each treatment arm and overall, based on data as observed. Subjects with missing values for compliance will not be included in the denominator.

10.0 Efficacy Analysis

10.1 General Considerations

General Considerations

All efficacy analyses will be performed on the ITT population, unless otherwise specified. To support the primary analysis, sensitivity analyses will be conducted for it using the mITT-GT and mITT-GT-VF populations.

Missing data will be imputed for analyses of the HCV RNA endpoints of SVR and virologic failure as described in Section 6.3 and for analyses of PROs as described in Section 6.3 and Section 10.9.

Plasma HCV RNA levels will be determined for each sample collected by the central laboratory using the Roche COBAS® AmpliPrep/COBAS® TaqMan® HCV Quantitative Test, v2.0. The lower limit of detection (LLOD) and lower limit of quantification (LLOQ) for this assay (regardless of genotype) are both 15 IU/mL.

HCV RNA results that are detectable but not quantifiable are reported as "< 15 IU/ML HCV RNA DETECTED" and those that are undetectable are reported as "HCV RNA NOT DETECTED" in the database.

The notation "HCV RNA < LLOQ" is used to represent all HCV RNA values < 15 IU/mL, including values reported as "HCV RNA NOT DETECTED" or "< 15 IU/ML HCV RNA DETECTED." HCV RNA \geq LLOQ are all quantifiable values of 15 IU/mL or greater.

Definitions for Efficacy Endpoints

A confirmed quantifiable value during treatment is defined as any two consecutive HCV RNA measurements \geq LLOQ (or 100 IU/mL for **Breakthrough**), either both during treatment or at the final treatment measurement and the next consecutive post-treatment measurement. A confirmed quantifiable post-treatment value is defined as any two consecutive post-treatment HCV RNA measurements \geq LLOQ.

Breakthrough = confirmed HCV RNA \geq 100 IU/mL after HCV RNA < LLOQ during the Treatment Period; or confirmed increase from nadir in HCV RNA (two consecutive HCV RNA measurements > 1 log₁₀ IU/mL above nadir) at any time point during the Treatment Period. A single breakthrough value (\geq 100 IU/mL or > 1 log₁₀ above nadir) followed by lost to follow-up also will be considered a breakthrough (i.e., will not require confirmation).

EOT failure = HCV RNA \geq LLOQ at end of treatment with at least 6 weeks of treatment, where the HCV RNA value must be collected on or after Study Drug Day 36 and study drug duration \geq 36 days.

On-treatment virologic failure = Breakthrough or EOT failure; if a subject meets both definitions of Breakthrough and EOT failure, he or she will be categorized as Breakthrough only.

SVR₄ = HCV RNA $<$ LLOQ in the SVR₄ window (4 weeks after the last actual dose of study drug) without any confirmed quantifiable (\geq LLOQ) post-treatment value before or during that SVR window.

SVR₁₂ = HCV RNA $<$ LLOQ in the SVR₁₂ window (12 weeks after the last actual dose of study drug) without any confirmed quantifiable (\geq LLOQ) post-treatment value before or during that SVR window.

SVR₂₄ = HCV RNA $<$ LLOQ in the SVR₂₄ window (24 weeks after the last actual dose of study drug) without any confirmed quantifiable (\geq LLOQ) post-treatment value before or during that SVR window.

Relapse₁₂ = confirmed HCV RNA \geq LLOQ between end of treatment and 12 weeks after last actual dose of study drug (up to and including the SVR₁₂ window) for a subject with HCV RNA $<$ LLOQ at Final Treatment Visit who completed treatment, excluding reinfection as described below.

Relapse₂₄ = confirmed HCV RNA \geq LLOQ within the SVR₂₄ window for a subject who achieved SVR₁₂ and has HCV RNA data available in the SVR₂₄ window, excluding reinfection.

Relapse_{overall} = confirmed HCV RNA \geq LLOQ between end of treatment and up to and including the last HCV RNA measurement collected in the Post-Treatment Period for a subject with HCV RNA $<$ LLOQ at Final Treatment Visit who completed treatment, excluding reinfection.

Virologic failure for SVR₁₂ = On-treatment virologic failure or Relapse₁₂.

Only subjects who have at least one post-treatment HCV RNA value will be included in analyses of relapse. For the analysis of relapse, completion of treatment is defined as any subject with study drug duration of 52 days or greater for Arm A, and 77 days or greater for Arm B. If the last available post-treatment value is \geq LLOQ, then the subject will be considered a relapse (i.e., will not require confirmation).

HCV reinfection is defined as confirmed HCV RNA \geq LLOQ after the end of treatment in a subject who had HCV RNA $<$ LLOQ at Final Treatment Visit, along with the post-treatment detection of a different HCV genotype, subtype, or clade compared with baseline, as determined by phylogenetic analysis of the NS3/4A or NS5A, and/or NS5B gene sequences. Reinfection in the case of the same HCV subtype is defined as a clade switch, as indicated by the lack of clustering between the baseline and post-treatment sequences by phylogenetic analysis. If phylogenetic analysis is not possible due to technical difficulties, HCV reinfection may be determined with a confirmed HCV genotype or subtype switch by the Versant HCV Genotype Inno-LiPA Assay v2.0 or Sanger assay.

Post-treatment relapse is defined as described earlier (**Relapse₁₂**, **Relapse₂₄**, **Relapse_{overall}**), and no genotype, subtype, or clade switch compared with baseline as determined by phylogenetic analysis of the NS3/4A or NS5A, and/or NS5B gene sequences. If phylogenetic analysis is not possible due to technical difficulties, the subject will be defined as having a post-treatment relapse unless an HCV genotype or subgenotype switch is confirmed by the Versant HCV Genotype Inno-LiPA Assay v2.0 or Sanger assay.

Reasons for SVR₁₂ Non-Response

Subjects who do not achieve SVR₁₂ (SVR₁₂ non-responders) will be categorized as having:

1. On-treatment virologic failure (see **On-treatment virologic failure** definition);

2. HCV reinfection (see definition described earlier);
3. Relapse₁₂;
4. Prematurely discontinued study drug with no on-treatment virologic failure (defined as any SVR₁₂ non-responder who prematurely discontinued study drug [study drug duration < 52 days for subjects in Arm A, and < 77 days for subjects in Arm B] and did not meet the **On-treatment virologic failure or HCV reinfection** definitions);
5. Missing follow-up data in the SVR₁₂ window (defined as any subject who completed study drug without data in the SVR₁₂ window after applying the imputation rules and not meeting the definitions of [1], [2], [3], or [4]);
6. Other (defined as any SVR₁₂ non-responder not meeting the definitions of [1] – [5]).

Reasons for SVR₂₄ Non-Response

Subjects who do not achieve SVR₂₄ (SVR₂₄ non-responders) will be categorized as having:

1. On-treatment virologic failure (see **On-treatment virologic failure** definition);
2. HCV reinfection;
3. Relapse₁₂;
4. Relapse₂₄;
5. Prematurely discontinued study drug with no on-treatment virologic failure (defined as any SVR₂₄ non-responder who prematurely discontinued study drug [study drug duration < 52 days for subjects in Arm A, and < 77 days for subjects in Arm B] and did not meet the **On-treatment virologic failure, HCV reinfection, Relapse₁₂, or Relapse₂₄** definitions);

6. Missing follow-up data in the SVR₂₄ window (defined as any subject who completed study drug without data in the SVR₂₄ window after applying the imputation rules and not meeting the definitions of [1], [2], [3], [4], or [5]);
7. Other (defined as any SVR₂₄ non-responder not meeting the definitions of [1] – [6]).

For the reasons for SVR₁₂ and SVR₂₄ nonresponse defined above, subjects are only to be counted in one category in the order shown above. Specifically, subjects who were SVR₁₂ or SVR₂₄ nonresponders meeting the definition of HCV reinfection will be counted in the reinfection category regardless of whether they meet the definition of prematurely discontinued study drug, Relapse₁₂ or Relapse₂₄.

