5.4.1.1 HCV Virologic Failure Criteria

The following criteria will be considered evidence of HCV virologic failure for the purposes of subject management:

- Confirmed increase from nadir in HCV RNA (defined as 2 consecutive HCV RNA measurement of $> 1 \log_{10}$ IU/mL above nadir) at any time point during study drug treatment.
- Confirmed HCV RNA ≥ 100 IU/mL (defined as 2 consecutive HCV RNA measurements ≥ 100 IU/mL) after HCV RNA $< \text{LLOQ}$ during study drug treatment.

When confirmatory testing is required, it should be completed as soon as possible and the subject should remain on study drug treatment until the virologic failure criteria has been confirmed. Subjects meeting the virologic failure criteria will be discontinued from study drug and will continue to be followed in the Post-Treatment Period for the emergence and persistence of resistant viral variants until 24 weeks post-treatment.

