8.0 Statistical Methods and Determination of Sample Size

8.1 Statistical and Analytical Plans

The primary analysis will occur after all subjects have completed the PT Week 12 Visit or prematurely discontinued treatment. The data for the primary analysis will be locked after data cleaning. Data after PT Week 12 will be added to a new version of the database which will be cleaned and locked at the end of the study.

SAS[®] (SAS Institute, Inc., Cary, NC) for the UNIX operating system will be used for all analyses. All confidence intervals will be two-sided with an alpha level of 0.05.

Descriptive statistics will be provided, such as the number of observations (N), mean, and standard deviation (SD) for continuous variables and counts and percentages for discrete variables.

Safety, and demographic analyses will be performed on all subjects who receive at least one dose of study drug.

Efficacy analyses will be performed on the intention-to-treat (ITT) population defined as all enrolled subjects who receive at least one dose of study drug, unless otherwise specified.

Sensitivity analyses of the primary efficacy endpoint, when applicable, will be performed on the intention-to-treat population modified to exclude subjects not of GT5, 6 according to phylogenetic analyses (mITT-GT), and on the mITT-GT population further modified to exclude subjects who did not achieve SVR₁₂ for reasons other than virologic failure (mITT-GT-VF).

No data will be imputed for any efficacy or safety analysis except for analyses of SVR endpoints (HCV RNA data). HCV RNA values will be selected for the analyses of all SVR endpoints (e.g., SVR₄, SVR₁₂, and SVR₂₄) based on defined visit windows. A backward imputation method will be used to impute missing responses for SVR analyses.

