4.2 Design Diagram

Study M16-126 is a Phase 3b, open-label, nonrandomized, multicenter study to evaluate the efficacy and safety of GLE/PIB in adults with chronic HCV GT5 or 6 infection, without cirrhosis or with compensated cirrhosis, who are either treatment-naïve or treatment-experienced with IFN or pegIFN with or without RBV or treatment-experienced with SOF plus RBV with or without pegIFN.

The study will enroll approximately 80 eligible subjects. A minimum of 15 GT5 and 30 GT6 subjects and up to approximately 16 subjects with compensated cirrhosis (regardless of GT) will be enrolled. Each subject will be assigned to one of two treatment arms based on their cirrhosis status. Non-cirrhotic subjects (Arm A) will be treated with GLE/PIB 300 mg/120 mg once daily for 8 weeks, while subjects with compensated cirrhosis (Arm B) will be treated with GLE/PIB 300 mg/120 mg once daily for 12 weeks.

Scheduled visits for subjects in the Treatment Period consist of Day 1 and Weeks 1, 2, 4, and 8 for all subjects and an additional Week 12 visit for subjects in Arm B. Subjects who complete or prematurely discontinue study drug will be followed for 24 weeks. During the Post-Treatment Period, all subjects will have visits at Post-Treatment Weeks 4, 12, and 24.

Figure 1. Study Schematic

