4.3 Sample Size

In Phase 2 and 3 studies, Study M14-868 and Study M14-172, GT 5 and 6 subjects were enrolled to demonstrate the pangenotypic efficacy of GLE/PIB across GT1-6 for the label

approved treatment duration. The current study, Study M16-126, serves to generate additional efficacy and safety data from GT 5 and 6 subjects in a wider geographic region. Therefore, no formal hypothesis will be tested in this study. The sample size of this study is determined based on operational considerations of enrolling subjects with less common HCV genotypes.

If the observed SVR₁₂ rate in this study is 97% among the expected 30 GT5 and 50 GT6 subjects, then the expected 95% confidence intervals (CIs) for the SVR₁₂ rate using the Wilson's score method¹ are (84.2%, 99.3%) and (88.2%, 99.1%), respectively, based on the Wilson's score CIs calculated for 1000 simulated samples of 30 GT5 and 50 GT6 subjects with an SVR₁₂ rate of 97% using SAS[®]. The Wilson's score method is expected to be used instead of the normal approximation method because the number of SVR₁₂ non-responders is expected to be less than 5 (see Section 10.3).

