10.4 Secondary Efficacy Analyses

The secondary efficacy endpoints are:

- The percentage of subjects with on-treatment virologic failure;
- The percentage of subjects with Relapse₁₂.

The number and percentage of subjects with on-treatment virologic failure and Relapse₁₂ in the ITT population will be summarized along with two-sided 95% Wilson score CIs by GT (GT5 and GT6) across treatment arms.

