10.7 Additional Efficacy Analyses

As additional analyses, the analyses of SVR₁₂ (as described in Section 10.3) and on-treatment virologic failure and Relapse₁₂ (as described in Section 10.4) in the ITT population and the sensitivity analyses of SVR₁₂ in the mITT-GT and mITT-GT-VF populations (as described in Section 10.5) will be performed for the overall population

across treatment arms and genotypes. For the SVR₁₂ endpoints, two-sided 95% CIs using both the normal approximation to the binomial distribution and the Wilson's score method will be calculated. For the other endpoints, only the two-sided 95% CI using Wilson's score method will be calculated.

The following additional efficacy endpoints will be summarized and analyzed for the ITT population, by GT (GT5 and GT6) across treatment arms and overall:

- The percentage of subjects with HCV RNA < LLOQ at each post-baseline visit in the Treatment Period (using data as observed);
- The percentage of subjects with SVR₄;
- The percentage of subjects with SVR₂₄;
- The percentage of subjects who relapsed after achieving SVR₁₂ (**Relapse₂₄**).
- The percentage of subjects with virologic failure through Post-Treatment Week 12 (i.e., the SVR₁₂ non-responders due to **on-treatment virologic failure** or **Relapse₁₂**)

For each of the above endpoints, a two-sided 95% CI using Wilson's score method will be calculated along with the number and percentage of subjects. Imputations for missing data will be performed as described in Section 6.3 for all the additional endpoints listed above except the first one.

For the overall ITT population and by GT, a summary of the subjects who completed treatment and relapsed (defined as **Relapse_{overall}**) will be prepared displaying the number and percentage of subjects relapsing overall and by the SVR visit window where the first relapse occurred (within the SVR₄, SVR₁₂, SVR₂₄ windows or after SVR₂₄ window), including the subject number and the SVR visit window corresponding to the first occurrence of relapse. A similar summary will be prepared for subjects who prematurely discontinued treatment and relapsed after having HCV RNA < LLOQ at their Final Treatment Visit.

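### SAP 10.4 can count an SVR12 responder as an on-treatment virologic failure, because EOT failure rests on one quantifiable value and the count is not limited to non-responders

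*SAP*

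**What the plan says.** **EOT failure (SAP 10.1).** The subject needs HCV RNA at or above LLOQ, with the timing given as "at end of treatment with at least 6 weeks of treatment, where the HCV RNA value must be collected on or after" a cut-off of Day 36, and a treatment duration of at least 36 days. The LLOD and LLOQ "for this assay (regardless of genotype) are both 15 IU/mL". The definition does not ask for a second value. The same section does define a confirmed on-treatment value as two consecutive quantifiable results, the second of which may be the first post-treatment sample. Breakthrough uses that confirmation, except when a single breakthrough value is followed by loss to follow-up.

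**On-treatment virologic failure (SAP 10.1 and 10.4).** This is Breakthrough or EOT failure. The first secondary endpoint is "The percentage of subjects with on-treatment virologic failure", summarised in the ITT population by genotype with Wilson intervals. SAP 10.7 repeats it for the overall population.

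**SVR12 (SAP 10.1).** The subject must be below LLOQ in the SVR12 window, with no confirmed quantifiable post-treatment value up to then. On-treatment values play no part.

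**Where the SAP does restrict to non-responders.** The table of reasons in SAP 10.1 covers SVR12 non-responders only. So does the additional endpoint in SAP 10.7, "The percentage of subjects with virologic failure through Post-Treatment Week 12", which takes non-responders whose reason is on-treatment failure or Relapse12.

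**Protocol.** Section 8.1.2.2 names on-treatment virologic failure as a secondary endpoint but does not define it.

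**The concern.** Take an Arm A subject with 20 IU/mL at Week 8 and results below LLOQ at Post-Treatment Weeks 4 and 12. This subject is a success in the primary endpoint and a failure in a secondary endpoint that most readers will take as one of the ways to miss SVR12.

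Two tables of the same report could then disagree. On-treatment virologic failure is a component of the 10.7 composite, yet the component could show one subject and the composite none. With a high expected SVR12 rate and 30 and 50 subjects per genotype, failure counts will be small, and a single subject changes what the secondary endpoint says.

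**Working it through.** **Inputs.** Intervals: "All confidence intervals will be two-sided with an alpha level of 0.05" (Protocol 8.1), so z = 1.96 and z² = 3.8415. Group sizes: "If the observed SVR₁₂ rate in this study is 97% among the expected 30 GT5 and 50 GT6 subjects" (SAP 4.3). Lower bounds on enrolment: "A minimum of 15 GT5 and 30 GT6 subjects" (SAP 4.2).

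**Step 1: reproduce the plan's own figures.**
- The protocol half-width z√(0.97 × 0.03 / n) gives 0.061 for n = 30 and 0.047 for n = 50, as Protocol 8.2 states.
- Wilson limits averaged over a Binomial(n, 0.97) distribution give (84.1%, 99.2%) for n = 30 and (88.2%, 99.1%) for n = 50. SAP 4.3 has (84.2%, 99.3%) and (88.2%, 99.1%) from 1000 simulated samples. The agreement is within 0.1 point. None of these figures is in dispute.

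**Step 2: apply the SAP definitions to every pattern.** Assume a treatment completer with one sample each at EOT, Post-Treatment (PT) Week 4 and PT Week 12, no reinfection, no Breakthrough, and PT Week 12 as the last value. The next-to-last column shows what would happen if EOT failure also required the next sample to be quantifiable.

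| EOT | PT4 | PT12 | SVR12 | EOT failure as written | EOT failure if confirmed | Relapse12 |
|---|---|---|---|---|---|---|
| < | < | < | yes | no | no | no |
| < | < | ≥ | no | no | no | yes |
| < | ≥ | < | yes | no | no | no |
| < | ≥ | ≥ | no | no | no | yes |
| ≥ | < | < | **yes** | **yes** | no | no |
| ≥ | < | ≥ | no | yes | **no** | **no** |
| ≥ | ≥ | < | **yes** | **yes** | **yes** | no |
| ≥ | ≥ | ≥ | no | yes | yes | no |

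Two patterns (rows 5 and 7) are both SVR12 responders and on-treatment failures as the SAP stands. In row 7 there is only one quantifiable post-treatment value, so it is not confirmed and SVR12 is met.

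**Step 3: what confirmation alone would do.** Row 7 stays in both categories. Row 6, a real rebound, would be neither EOT failure nor Relapse12, because Relapse12 requires a value below LLOQ at the Final Treatment Visit. The subject would fall into the Other category and leave mITT-GT-VF. If all other GT5 subjects respond, SVR12 in that population would go from 29/30 to 29/29.

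**Step 4: size per subject.** The Wilson limits are [p + z²/(2n) ± z√(p(1 − p)/n + z²/(4n²))] / (1 + z²/n). For zero events the upper limit reduces to z²/(n + z²), for example 3.8415/33.8415 = 11.4% for n = 30.

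| Group | Not counted | One such subject counted |
|---|---|---|
| GT5, n = 30 | 0/30: 0% (0 to 11.4%) | 1/30: 3.3% (0.6 to 16.7%) |
| GT6, n = 50 | 0/50: 0% (0 to 7.1%) | 1/50: 2.0% (0.4 to 10.5%) |
| GT5 minimum, n = 15 | 0/15: 0% (0 to 20.4%) | 1/15: 6.7% (1.2 to 29.8%) |

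**Step 5: how likely is one.** The documents give no rate. As an assumption only, if a fraction q of subjects have a quantifiable EOT value and later meet SVR12, the chance of at least one is 1 − (1 − q)ⁿ. For q from 0.2% to 2% this is 6% to 45% in 30 GT5 subjects and 10% to 64% in 50 GT6 subjects.

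**The case against.** The best defence is that 10.4 and 10.7 are different endpoints with stated populations. A subject still quantifiable at the last treatment visit has not shown end-of-treatment response, whatever happens later, and any difference between the two counts can be traced to the definitions. There is no hypothesis test (SAP 10.2), the primary endpoint is untouched, the error can only overstate failure, and nothing shows that it will occur.

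Most of that stands and limits the weight of the point. It does not remove it. The SAP never says that the overlap is intended, and in both other places where it reports on-treatment failure as a cause of non-response it restricts to SVR12 non-responders.

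A reader might also infer stronger claims that the documents do not support:
- **That the SAP contradicts the protocol's failure criteria.** Protocol 5.4.1.1 opens with "The following criteria will be considered evidence of HCV virologic failure for the purposes of subject management". It governs conduct and does not define the secondary endpoint, so the SAP's added definition breaks no protocol rule.
- **That true relapses are lost.** A subject quantifiable at EOT who is negative at PT Week 4 and rebounds by PT Week 12 is labelled on-treatment failure rather than Relapse12. The subject is still a virologic failure in the reasons table, the 10.7 composite and mITT-GT-VF.
- **That 36 days against 6 weeks (42 days) is part of the fault.** The operational cut-off is explicit, may be a visit allowance, and does not create the overlap.

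**Conclusion.** The concern holds as a gap in definition. As written, an SVR12 responder with a quantifiable EOT value is counted as an on-treatment virologic failure in SAP 10.4 and in its overall-population repeat in 10.7, and the 10.4 count can exceed the composite that contains it. The effect per subject is 3.3 percentage points in GT5 at n = 30 and 2.0 points in GT6 at n = 50, with the upper limit moving from 11.4% to 16.7% and from 7.1% to 10.5%.

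This rests on a literal reading of SAP 10.1 and 10.4 and on the planned group sizes. Whether such a subject will occur is unknown. The overlap does not reach the primary SVR12 rate, the reasons for non-response, the 10.7 composite or mITT-GT-VF.

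**What to change.** In SAP 10.4, and in its repeat for the overall population in 10.7, count on-treatment virologic failure among SVR12 non-responders only and keep the ITT denominator. This matches the reasons table in 10.1 and the composite in 10.7. List separately any SVR12 responder with a quantifiable EOT value. The list should also show any responder who met Breakthrough, since the same restriction would remove that subject from the count.

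If the sponsor prefers to add a confirmation requirement to EOT failure, that cannot be done alone (step 3 of the working). The condition of a value below LLOQ at the Final Treatment Visit, in Relapse12, in the overall relapse definition and in reinfection, must be amended at the same time, so that a subject with an unconfirmed EOT value and a later rebound remains a virologic failure. The pattern of quantifiable values at EOT and PT Week 4 followed by SVR12 would still need the restriction to non-responders.

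The preferred change costs SAP wording, one programming condition and one listing. It needs no new data. Its downside is that the on-treatment failure count can only fall or stay the same, and the listing makes that visible.
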